## 7. RESEARCH QUESTION AND OBJECTIVES

The overall aim of the study is to describe how prescribing of NOMAC and CMA has changed following the introduction of EU-level RMM related to the risk of meningioma ('restrictions to use' from now on) in November 2022. To contextualise findings, changes of other relevant drug classes will also be described.

The specific objectives are:

- 1. To assess the monthly prevalence and incidence of use of drug classes of interest before and after the implementation of the restrictions of use.
- 2. To assess duration of use and cumulative dose of products containing NOMAC or CMA before and after the implementation of restrictions of use.
- 3. To describe characteristics of users of relevant drug classes before and after implementation of the restrictions of use.
- 4. To describe the line of treatment (2nd/3rd versus 1st) in users of products containing NOMAC or CMA before and after the implementation of the restrictions of use
- 5. To describe the frequency of patients who develop meningioma during treatment with products containing NOMAC or CMA, and those who discontinue or switch to alternative treatments before and after implementation of the restrictions of use.
- 6. To assess the impact of the restrictions of use adopted in 2018 and 2022 in incident prescriptions of products containing NOMAC or CMA.

Objective 1 and 3 will be assessed for all relevant drug classes. These will include progestogen and estrogen combination products, progestogens that are pregnadien derivates, and medroxyprogesterone-containing products.

Objective 2 and 6 will focus on products containing NOMAC or CMA. Objective 4 and 5 will focus on these two compounds but will consider relevant drug classes to establish line of treatment or switches.

A description of the proposed objectives is described in Table 1.

**Table 1.** Primary and secondary research questions and objective.

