#### Progestogens of interest:

- Medroxyprogesterone (WHO ATC G03AC06, G03DA02, G03AA17, G03FA12, G03FB06, G03AA08)
- NOMAC (WHO ATC G03AA14, G03DB04, G03FB12)
- CMA (WHO ATC G03AA15, G03AB07, G03DB06, G03FB03)

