#### 6. RATIONALE AND BACKGROUND

Medicines containing nomegestrol acetate (NOMAC) or chlormadinone acetate (CMA) are synthetic progestins with antiandrogenic effects. Approved indications for NOMAC and CMA in monotherapy or in combination with oestrogens differ between different strengths and different countries. In general, they are indicated for gynaecological and menstrual disorders, hormone replacement therapy (HRT) and, at lower doses, as hormonal contraception.

Meningioma is a rare tumour that forms from the meninges. Known risk factors for meningioma are being female, exposure to ionising radiation and neurofibromatosis type 2.(1) Recently published studies have found a dose-dependent association between NOMAC or CMA and meningioma.(2-5) The hazard ratio (HR) of intracranial meningioma adjusted for age was 4.5 (3.5-5.7) and 4.4 (95% CI 3.4-5.8) among women exposed to NOMAC and CMA, respectively.(2, 3) The risk of meningioma increased with dose and duration of treatment and diminished one year after the discontinuation of treatment. Prolonged exposure to progestogens other than NOMAC such as cyproterone acetate (6) and medroxyprogesterone acetate (7) has also been linked to an increased risk of meningioma.

The risk of meningioma associated with NOMAC is known since 2018 and has been assessed within different regulatory procedures.(8) In October 2018, the Pharmacovigilance Risk Assessment Committee (PRAC) recommended to amend the product information of monotherapy products containing NOMAC to include the contraindication for patients who have, or have had, meningioma. PRAC also recommended permanently discontinuing treatment in patients who develop meningioma. In 2020, the product information of products containing NOMAC in combination with oestradiol was updated with similar contraindications and warnings.

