#### 8.6.2 Outcomes

Outcomes will be considered for the population-level DUS (objective 1) and will consist of the 2 drug classes and 3 progestogens of interest described in "8.6 Variables". They will also be considered to study records of drug classes of interest not containing NOMAC nor CMA for objectives aiming to assess line of treatment (objective 4) and switching (objective 5). Meningioma will also be considered as an outcome for Objective 5.

<sup>2 IP = inpatient, OP = outpatient

<sup>3 Specify whether a diagnosis code is required to be in the primary position (main reason for encounter)

P3-	C3-0	106	Study	Protoco	ı

Version: V4.0

Dissemination level: Public

The operational definition of the outcomes is presented in the **Table 8**. Preliminary concepts for the exposures are detailed in **Appendix I**.

Authors: [name], [name], [name], [name], [name] Version: V4.0

Dissemination level: Public

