## Table 8. Operational definitions of outcomes.

Outcome name 	Details	Primary outcome?	Type of outcome	Washout window 	Care Settings 	Code Type⁴	Applied to study populations
Progestogen and estrogen combination products	For incidence/prevalence calculations (Objective 1).	Yes	Count	[-365, -1]	IP, OP	RxNorm	General population (objective 1 and 6)
Progestogens that are pregnadien derivates	For incidence/prevalence calculations (Objective 1).	Yes	Count	[-365, -1]	IP, OP	RxNorm	General population (objective 1 and 6)
Medroxyprogesterone	For incidence/prevalence calculations (Objective 1).	Yes	Count	[-365, -1]	IP, OP	RxNorm	General population (objective 1 and 6)
NOMAC	For incidence/prevalence calculations (Objective 1 and 6).	Yes	Count	[-365, -1]	IP, OP	RxNorm	General population (objective 1 and 6)
СМА	For incidence/prevalence calculations (Objective 1 and 6).	Yes	Count	[-365, -1]	IP, OP	RxNorm	General population (objective 1 and 6)
Progestogen and oestrogen combination products not containing NOMAC or CMA	To assess line of treatment and switches to alternative treatments (Objective 4 and 5).	Yes	Binary	N/A	IP, OP	RxNorm	New users of NOMAC or CMA (objective 2, 4 and 5)
Progestogens that are pregnadien derivates not containing NOMAC or CMA	To assess line of treatment and switches to alternative treatments (Objective 4 and 5).	Yes	Binary	N/A	IP, OP	RxNorm	New users of NOMAC or CMA (objective 2, 4 and 5)
Meningioma	Diagnosis of meningioma	Yes	Binary	[-Inf,-1]	IP, OP	SNOMED	New users of NOMAC or CMA (objective 2, 4 and 5)

<sup>1 NOMAC = nomegestrol, CMA = chlormadinone

<sup>2 For outcomes relative to objective 1 and 6, the washout window will be applied for incidence calculations only.

 $^{3}$  IP = inpatient, OP = outpatient, ED = emergency department, OT = other, n/a = not applicable.

<sup>4 RxNorm codes will be identified based on the vocabulary hierarchy, with ATC codes being ancestors.

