## Objective 5:

[figure not shown]
We will describe the number and proportion of patients that follow different treatment strategies in the 180 days following the end of treatment. These strategies are defined as:

- Restart the same treatment
- Switch to a different treatment
- Restart and switch to a different treatment
   Discontinued treatment (not treated, neither with the original treatment nor any potential switch)

For this objective (time period comparison), both incident and prevalent users will be considered. The proportion of individuals following each treatment strategy (e.g. switching) will be calculated using the number of people exposed to the product of interest during the time period under study (e.g. pre-intervention) as the denominator regardless of when the initiation started.

Figure 2 illustrates some of these scenarios.

**Figure 2.** Outcomes after the drug exposure of interest (in blue) over different time periods.

Source: DrugUtilisation R package website (22)

The number of meningioma cases occurring any time during treatment with NOMAC or CMA, and in the six months prior to the end of treatment will also be reported. For cases identified in the six months prior, we will report the treatment strategy followed after treatment (i.e. restart, switch, both, or discontinuation).

NOMAC and CMA will be assessed separately. Results will be reported overall and stratified by study period (pre- vs. postintervention) and WHO 5th ATC level codes (if counts allow). For the pre- and post-intervention comparison, treatments initiated during the 180 days before the intervention will not be considered, to ensure sufficient time for assessing outcomes (e.g., switches, discontinuations) prior to the intervention.

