# **Drug classes:**

Drug class	Analysis	WHO ATC 4 th level codes 	WHO ATC 5 th level codes 
Progestogens that are pregnadien derivates	Objective 1	G03DB	All descendants included
Progestogen and oestrogen combination products	Objective 1	G03AA, G03AB, G03FA, G03FB	All descendants included

Authors: [name], [name], [name], [name], [name]

Version: V4.0

Dissemination level: Public

		T .	I
Medroxyprogesterone 	Objective 1	N/A	G03AC06, G03DA02,
			G03AA17, G03FA12,
			G03FB06, G03AA08,
			L02AB02
Nomegestrol	Objective 1 and 6	N/A	G03AA14, G03DB04,
			G03FB12
Chloramidinone	Objective 1 and 6	N/A	G03AA15, G03AB07,
	-		G03DB06, G03FB03
Progestogen and estrogen	Objective 4 and 5	G03AA, G03AB,	All descendants
combination products not	-	G03FA, G03FB	included, except:
containing nomegestrol or			G03AA14, G03AA15,
chlormadinone.			G03AB07, G03FB12 and
			G03FB03
Progestogens that are	Objective 4 and 5	G03DB	All descendants
pregnadien derivates not			included, except:
containing nomegestrol or			G03DB04 and G03DB06.
chlormadinone.			
Drug classes of interest (any)	Objective 3	G03AA, G03AB,	All descendants
		G03DB, G03FA, G03FB	included

<sup>1 All descendants included.

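### The code lists for Objectives 3 to 5 omit single-agent medroxyprogesterone (G03AC06, G03DA02), although the protocol text counts the drug as relevant, so some switching, line-of-treatment and new-user classifications will be wrong

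*Protocol*

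**What the plan says.** Section 7 states that Objectives 1 and 3 cover all relevant drug classes and continues: "These will include progestogen and estrogen combination products, progestogens that are pregnadien derivates, and medroxyprogesterone-containing products". On the next two objectives it says: "Objective 4 and 5 will focus on these two compounds but will consider relevant drug classes to establish line of treatment or switches". Section 8.6.2 describes outcomes that "will consist of the 2 drug classes and 3 progestogens of interest described in" Section 8.6, where medroxyprogesterone is one of the three progestogens, and then carries these outcomes over to Objectives 4 and 5. For Objective 3, Section 8.6.1 lists medroxyprogesterone among the exposures, and Table 7 covers classes and progestogens alike.

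The abstract gives the codes: "Medroxyprogesterone (WHO ATC G03AC06, G03DA02, G03AA17, G03FA12, G03FB06, G03AA08".

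The operational lists are narrower. In Table 8 only two drug rows carry the purpose "To assess line of treatment and switches to alternative treatments (Objective 4 and 5": combination products and pregnadien derivates, each without NOMAC or CMA. The medroxyprogesterone row there serves Objective 1. Appendix I does the same. Its Objective 4 and 5 rows are the four combination groups, and G03DB without "G03DB04 and G03DB06". Its Objective 3 row is those same five groups, and medroxyprogesterone is tagged for Objective 1 alone.

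Section 8.8 defines one Objective 5 category as "Discontinued treatment (not treated, neither with the original treatment nor any potential switch", assessed over 180 days after the end of treatment.

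**The concern.** Switching, discontinuation and first-line use are all read off the code lists. If a drug that the text calls relevant is missing from a list, women who use it are not shown as a gap. They are placed in another category, as untreated in Objective 5 or as first-line in Objective 4.

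This matters more for medroxyprogesterone than for an arbitrary progestogen, because Section 6 says that prolonged exposure to "medroxyprogesterone acetate (7) has also been linked to an increased risk of meningioma". In a study of whether risk minimisation worked, replacement of NOMAC or CMA by another progestogen linked to meningioma is a result worth seeing. As the lists stand, replacement by medroxyprogesterone alone would be reported in Objective 5 as stopping treatment. Section 8.8 compares discontinuation and switching separately before and after the intervention by standardised mean difference, so both comparisons are affected.

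**Working it through.** The plan gives no figure to reproduce. The check is a match of codes, followed by the protocol's own category rules.

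**Step 1: code match.** Inputs are the six non-oncological medroxyprogesterone codes (abstract and Appendix I), the five 4th-level groups in Appendix I (G03AA, G03AB, G03DB, G03FA, G03FB) and the listed NOMAC and CMA exclusions. A code is captured if its first five characters match a group and it is not excluded.

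| Code | Objective 3 list | Objective 4 and 5 lists |
|---|---|---|
| G03AA08 | yes | yes |
| G03AA17 | yes | yes |
| G03FA12 | yes | yes |
| G03FB06 | yes | yes |
| G03AC06 | no | no |
| G03DA02 | no | no |

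Four of six are captured and two of six are not. The oncological code L02AB02 is also outside the lists, which agrees with the intention to leave it out where possible. Adding the two missing codes gives six of six.

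**Step 2: does another passage repair the gap?** Table 1 places medroxyprogesterone, including medroxyprogesterone alone, under pregnadien derivates for Objective 3. That class is coded G03DB only, and no medroxyprogesterone code begins with G03DB, so the wording does not bring the two codes in.

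**Step 3: consequences under the protocol's rules.**
- Objective 5: a woman who moves to G03AC06 or G03DA02, with no restart and no other listed treatment within 180 days, is discontinued instead of switched. If she also restarts, she is counted as restart only, instead of restart and switch. If she also receives a listed class, she is still counted as a switch.
- Objective 4: a woman whose only earlier alternative treatment was one of these codes is first-line.
- Objective 3: a first prescription of one of these codes does not bring a woman into the cohort, and earlier use does not trigger the exclusion for prior use in Table 6.

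**Step 4: size.** Let m be the fraction of women, on the Objective 5 denominator, who move to one of the two codes. Those who also restart or receive a listed class are not moved into the discontinued category, so the shift from switch to discontinued is at most m.

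The documents give no value for m. As an assumed illustration, let s be the true share who switch without restarting, and q the share of these whose only new treatment is one of the two codes. The shift is then s × q:
- s = 10%, q = 5%: 0.10 × 0.05 = 0.005, or 0.5 percentage points
- s = 20%, q = 10%: 0.20 × 0.10 = 0.02, or 2 points
- s = 30%, q = 25%: 0.30 × 0.25 = 0.075, or 7.5 points

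**The case against.** For Objectives 4 and 5 the omission can be read as a deliberate narrower scope. In Section 7 the sentence naming medroxyprogesterone follows the one on Objectives 1 and 3, and the sentence on Objectives 4 and 5 lacks the word *all*. Section 8.6 separates two drug classes from three progestogens and puts medroxyprogesterone among the latter. Table 8 and Appendix I agree with each other. This has some force: for these two objectives the conflict rests on the phrase about relevant classes in Section 7 and on the carry-over in Section 8.6.2. But Section 7 itself calls medroxyprogesterone products a relevant class, and Section 8.6.3 lists the drug under drug classes of interest. No passage states or justifies leaving it out. For Objective 3 this defence is not available.

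Appendix I is labelled preliminary. That helps most for Objective 3, where Table 7 already has the drug. It does not help for Objectives 4 and 5, because Table 8 is main text and has the same gap.

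Medroxyprogesterone has its own incidence and prevalence series in Objective 1, so a population-level rise would be visible. That series cannot show which women came from NOMAC or CMA, and it does not correct the categories in Objectives 4 and 5.

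Section 6 also links cyproterone to meningioma, and the alternative-treatment rows do not name it. So the safety argument is not unique to medroxyprogesterone. The contradiction is, because Section 7 names medroxyprogesterone as relevant.

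A reader might infer that the error favours the study hypotheses. The documents do not support that. The Objective 5 hypothesis expects both switches and discontinuations to rise, and the error raises one at the expense of the other. In Objective 4 it overstates first-line use, which is hypothesised to fall.

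**Conclusion.** The gap is real and confined to G03AC06 and G03DA02. The inconsistency is firm for Objective 3. For Objectives 4 and 5 it follows from the wording of Sections 7 and 8.6.2, and the operational tables should be reconciled with that wording.

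Applied as written, the lists overstate discontinuation and understate switching, overstate first-line use, and leave some new users out of the Objective 3 cohort while admitting some women who are not first-time users. The shift in Objective 5 is bounded above by m, which the documents do not give; the 0.5 to 7.5 points shown rest entirely on assumed shares.

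Two stronger readings should be avoided. Medroxyprogesterone is not missing altogether, since its oestrogen combinations are captured. And m is not the exact error, since women who also restart or receive a listed class are not counted as discontinued.

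**What to change.** In Table 8 and Appendix I, add G03AC06 and G03DA02 as a separate alternative-treatment row for Objectives 4 and 5, and report it as its own switch category in Objective 5. Add the same codes to the Appendix I list for Objective 3. Keep L02AB02 out where possible, as already planned. Correct the Table 1 entry that places the drug under pregnadien derivates.

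If leaving it out of Objectives 4 and 5 is deliberate, correct Sections 7 and 8.6.2 instead, and report that the discontinued and first-line categories include women using medroxyprogesterone alone.

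The cost is small, because both codes are already listed for Objective 1. The one downside is that the limitations section uses medroxyprogesterone as its example of a drug whose ATC codes carry different indications and notes remaining ATC-to-RxNorm inconsistencies. Some oncological products may therefore not separate cleanly, and the report should say so.

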#### A. Primary research question and objective.

Objective:	Objective 1: To examine incidence/prevalence of drug classes of interest.
	Objective 2: To assess duration of use and cumulative dose of products containing NOMAC or CMA.
	Objective 3: To describe users of relevant drug classes.
	Objective 4: To describe the line of treatment in users of products containing NOMAC or CMA.
	Objective 5: To describe the frequency of patients who develop meningioma during treatment with products containing NOMAC or CMA,

Authors: [name], [name], [name], [name], [name] Version: V4.0

Dissemination level: Public

	and the frequency of users who discontinue or switch to alternative treatments.
	Objective 6: To assess the impact of the restrictions of use in incident prescriptions of products containing NOMAC or CMA.
	All objectives will be focused on comparing changes before and after the implementation of restrictions.
Hypothesis:	Objective 1: N/A, descriptive analysis.
	Objective 2: Cumulative dose and duration of treatments with NOMAC or CMA will be lower after the implementation of restrictions.
	Objective 3: The number of new users of NOMAC or CMA will be reduced after the implementation of restrictions.
	Objective 4: The number of users initiating NOMAC or CMA as first-line treatment will be reduced after the implementation of restrictions.
	Objective 5: The number of switches and discontinuations from NOMAC or CMA to other drug classes will increase after the implementation of restrictions.
	Objective 6: The incidence of NOMAC or CMA will be reduced after the implementation of restrictions, especially for high-dose products. This reduction will not be observed for other drug classes of interest.
Population:	All objectives: The study population will be restricted to females aged >10 years old with >1 year of prior data history available.
	Additional criteria:
	Objective 1 (subgroup analysis): Individuals with a prior history of meningioma.
	Objective 2, 4 and 5: Individuals newly exposed to products containing NOMAC or CMA.
	Objective 3: Individuals newly exposed to drug classes of interest.
Exposure:	Objective 1: N/A
	Objective 2: First-ever prescription of NOMAC or CMA (assessed separately).
	Objective 3: First-ever prescription of drug classes of interest (any), including:
	- Combined hormonal contraceptives

Authors: [name], [name], [name], [name], [name] Version: V4.0

Dissemination level: Public

	
 
Progestogens that are pregnadien derivates (including medroxyprogesterone and medroxyprogesterone alone)
 

	- Progestogen and oestrogen combination products.
	Objective 4: Same as Objective 2.
	Objective 5: Same as Objective 2.
	Objective 6: N/A
Comparator:	Before vs. After the implementation of restrictions
Outcome:	Objective 1: Prescribing of drug classes of interest (assessed separately)
	Objective 2: N/A (treatment duration and cumulative use of the exposure).
	Objective 3: N/A (characterisation of users)
	Objective 4: Prescribing of alternative treatments not containing NOMAC or CMA (assessed retrospectively to identify line of treatment).
	Objective 5: Number of patients diagnosed with meningioma during treatment and number of patients discontinuing treatment or switching to alternative treatments not containing NOMAC or CMA 180 days after the end of the index treatment.
	Objective 6: Prescribing of products containing NOMAC or CMA (assessed separately).
Time:	01/01/2010 to end of data availability
Setting:	Routinely collected data from 3 databases in 3 European countries.
Main measure of effect:	Objective 1:
	Incidence rates (new prescriptions per 100,000 person-years of the population at risk) and prevalence (proportions).
	Objective 2 to 5:
	- Objective 2: Median with minimum, maximum and interquartile range.
	- Objective 3-5: Counts and proportions
	
 
All objectives: Standardised Mean Differences (SMD) for comparing changes before and after the implementation of restrictions.
 

	Objective 6:
	Risk ratios derived from the interrupted time series analysis (ITS). ITS will be based on results obtained as part of Objective 1.

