#### **Covariates for stratification:**

Covariates for stratification will vary across objectives and will include:

- Age group:
   10-17, 18-34, 35-49, 50-64, +65 years.
- Indication:

Non-HRT vs. HRT. Indication will be assessed using age as a proxy (non-HRT in women aged 10-49 years, HRT in women aged >50 years).

- Dose:
  - High- vs low- dose, for NOMAC or CMA only. For NOMAC, high doses will include amounts from 3.75mg to 5mg. For CMA, high doses will include amounts from 5mg to 10mg. Low doses will be any amounts less than those specified.
- WHO 5th ATC level codes:
  - For NOMAC or CMA only, if counts allow. For NOMAC codes included will be: G03AA14, G03DB04, G03FB12. For CMA, codes included will be: G03AA15, G03AB07, G03DB06, G03FB03.
- Time period:
  - Preintervention: from start date to October 2022; Postintervention: from February 2023 to study end.

See below which covariates apply according to each objective.

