#### Objective 2-5:

For objectives 2 to 5, SMD of each of the covariates for the comparison of drug users in the pre-RMM and post-RMM period as a measure of the impact of the profile of drug users. These covariates will include: duration and cumulative dose (objective 2), patient characteristics (objective 3) and line of treatment (objective 4). For patient characteristics, only conditions will be compared, with the assessment window set as any time prior to 1 day before the index date. For objective 5, covariates will include the proportion of patients diagnosed with meningioma during treatment, and the proportion of patients who discontinue or switch to alternative treatments (assessed separately).

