#### A. Primary analysis

Hypothesis:	Objective 1: Not applicable, descriptive analysis.
	Objective 2: Cumulative dose and duration of treatments with NOMAC or CMA will be lower after the implementation of restrictions.
	Objective 3: The number of new users of NOMAC or CMA with prior history of meningioma will be reduced after the implementation of restrictions.
	Objective 4: The number of users initiating NOMAC or CMA as first-line treatment will be reduced after the implementation of restrictions.
	Objective 5: The number of discontinuations and switches from NOMAC or CMA to other drug classes will increase after the implementation of restrictions.
	Objective 6: The incidence of NOMAC or CMA will be reduced after the implementation of restrictions, especially for high-dose products. This reduction will not be observed for other drug classes of interest.
Exposure contrast:	Objective 1: Not applicable, descriptive analysis.
	Objective 2: Pre-intervention (1-year period) vs. Post-intervention (1-year period)
	Objective 3 to 6: Pre-intervention vs. Post-intervention
Outcome:	Objective 1: Incidence rates and prevalence of drug classes of interest
	Objective 2: Cumulative dose and treatment duration of NOMAC or CMA.

Authors: [name], [name], [name], [name], [name]

Version: V4.0

Dissemination level: Public

	Objective 3: Number and characteristics of users of drug classes of interest.
	Objective 4: Line of treatment when initiating NOMAC or CMA.
	Objective 5: Diagnosis with meningioma during treatment. Discontinuations and switches
	from treatments with NOMAC or CMA to others.
	Objective 6: Incidence rates of NOMAC or CMA.
	Drug classes of interest, NOMAC and CMA will be assessed separately.
Analytic software:	R
Model(s):	Objective 1: Not applicable, descriptive analysis.
	Objective 2 to 5: Standardised mean differences.
	Objective 6: Segmented regression (Poisson models).
Confounding adjustment method	
	Stratification.
Missing data methods	
	The absence of a record for a condition or medication will be considered as the absence of the disease or use of the medication.
Subgroup Analyses	
	Objective 1: Age groups, indication, study period. For NOMAC or CMA only: dose, WHO ATC 5 th level (if counts allow). A subgroup analysis will be performed restricting the study population to individuals with a prior history of meningioma.
	Objective 2: Study population, indication, study period.
	Objective 3: Study period.

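### Objective 3 carries two different hypotheses, and Objectives 3 and 4 predict falling numbers of users over periods of very unequal length, while the planned pre/post comparison is of shares

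*Protocol*

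**What the plan says.** **Hypotheses.** Section 7, Table 1, states "Objective 3: The number of new users of NOMAC or CMA will be reduced after the implementation of restrictions". Section 8.8, Table 11, states instead "Objective 3: The number of new users of NOMAC or CMA with prior history of meningioma will be reduced after the implementation of restrictions". Both tables give Objective 4 the same hypothesis: "The number of users initiating NOMAC or CMA as first-line treatment will be reduced after the implementation of restrictions".

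**Periods.** Section 8.6.3 defines them as "Preintervention: from start date to October 2022; Postintervention: from February 2023 to study end", and Table 9 agrees. Table 11 applies this full contrast: "Objective 3 to 6: Pre-intervention vs. Post-intervention". Windows of equal length are specified for Objective 2 only (Section 8.8).

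**Measures.** For Objectives 3 to 5, Table 1 lists counts and proportions, plus the SMD for the change across the intervention. Section 8.8 (Objective 2-5) and Table 11 also name the SMD as the pre/post comparison. For Objective 3 it is limited: "For patient characteristics, only conditions will be compared, with the assessment window set as any time prior to 1 day before the index date".

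**Objective 3 cohort.** Section 8.4, Table 4 and Table 6 define it as first-ever users of any drug class of interest, with the washout applied to all classes combined. Section 8.6.3 stratifies it by time period only. The abstract's list of exposures names NOMAC or CMA alone for this objective, which does not match the main text.

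**The concern.** The two Objective 3 hypotheses are different claims. One is about total uptake. The other is about whether women with a history of meningioma are still being started on these products. Either can hold while the other fails, and the protocol does not say which one Objective 3 is meant to assess.

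The word *number* adds a second problem. Over a long pre-period and a short post-period, a raw count of starters will almost always be lower afterwards, whether or not prescribing changed. The planned SMD avoids this because it compares shares, but it then answers a different question from the one the hypothesis asks.

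The proportion of starters with prior meningioma bears on the contraindication, and the proportion of first-line starts bears on the first-line restriction. If the report judges the hypotheses as worded, it could announce support for both on the strength of period length alone.

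**Working it through.** The protocol gives no sample size, power or expected count for Objectives 3 and 4, so there is no figure of its own to reproduce. The check covers period lengths, and then what the SMD measures.

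**Inputs.** Study start: 1 January 2010 (Section 8.3, used for Germany), 2012 for Belgium and 2017 for Croatia (Section 11). Pre-period end: 31 October 2022. Post-period start: 1 February 2023. Data locks (Table 3): 30 September 2023, 31 December 2023 and 17 November 2023. One month = 30.4375 days.

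**Fall in a raw count at an unchanged monthly rate** = 1 − (post months ÷ pre months):

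| Database | Pre | Post | Ratio | Fall in count |
|---|---|---|---|---|
| Germany | 154.0 | 8.0 | 19.4 | 94.8% |
| Belgium | 130.0 | 11.0 | 11.8 | 91.6% |
| Croatia | 70.0 | 9.5 | 7.3 | 86.4% |

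(Ratios and falls use unrounded months.) The ratio is also the factor by which the monthly rate would have to rise before the post count stopped being lower.

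**Sensitivity to the 365-day history rule.** If it removes the first year of data in Belgium and Croatia, the pre-periods become 118.0 and 58.0 months, the ratios 10.8 and 6.1, and the falls 90.7% and 83.6%. No such adjustment is made for Germany, where records go back to 1992 (Section 8.2).

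**Sensitivity to a later data cut.** Assume data to March 2025, a post-period of 26 months. The ratios are 154 ÷ 26 = 5.9, 130 ÷ 26 = 5.0 and 70 ÷ 26 = 2.7. The falls at a constant rate are 83%, 80% and 63%.

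**What the SMD responds to.** For a binary variable, SMD = (p₂ − p₁) ÷ √[(p₁(1 − p₁) + p₂(1 − p₂)) ÷ 2]. Assume 100 German starters a month before the restrictions, 60% of them first-line, so 154 × 60 = 9,240 first-line starts in the pre-period:

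| After the restrictions | First-line starts per month | SMD | Raw post count (8 months) |
|---|---|---|---|
| Rate halves, share stays 60% | 60 → 30 | 0 | 240 |
| Rate halves, share rises to 70% | 60 → 35 | +0.21 | 280 |
| Rate doubles, share stays 60% | 60 → 120 | 0 | 960 |

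The raw count falls in all three rows, including the one where first-line starts double. The SMD is zero in both the halving and the doubling at a constant share, and points upward when the monthly number falls but the share rises. Neither quantity tests a change in the number of first-line starters.

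**Objective 3.** The SMD covers prior conditions only, so the Table 1 version (number of new users) is not compared by it at all. The Table 11 version concerns NOMAC and CMA starters, whereas the SMD is computed in first users of all classes combined. Because of the combined washout, that cohort also leaves out any woman who took another listed product before starting NOMAC or CMA.

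**The case against.** The strongest reply is that the analysis is sounder than the hypothesis wording. Counts and proportions are listed as main measures, and results are stratified by period, so readers will see the first-line shares before and after. No passage plans a test that sets raw totals side by side. Uptake is assessed properly elsewhere, by monthly incidence rates in Objective 1 and segmented regression in Objective 6. The study's stated aim is to describe. All of this stands, and it makes the fault one of mismatch between hypothesis and measure, not of missing data.

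The reply also limits the size. Table 3 gives the last update, the code is to be run in March/April 2025, and the Objective 2 post-window reaches January 2024, later than any listed lock. The 86% to 95% falls therefore apply to the listed locks only.

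Two stronger readings are tempting. A reader might infer that the protocol's own test is met by construction. It is not, because the named comparison is the SMD; the artefact arises only if the hypotheses are judged literally on counts. A reader might also infer that the SMD would declare no difference even if prescribing to women with meningioma stopped. For a rare condition the SMD is indeed small: at an assumed prior share of 0.1% falling to zero it is 0.045 in absolute value. But the protocol gives neither that share nor any SMD threshold, so no such declaration follows. Section 11 already concedes that meningioma counts are too few for formal analysis.

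What survives is that two tables disagree on one objective, and that the wording of both objectives does not match the comparison planned for them.

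**Conclusion.** The point holds, and the wording should be corrected. Tables 1 and 11 contradict each other on Objective 3, which can be seen from the text without any assumption. Objectives 3 and 4 predict lower numbers over periods whose lengths differ about 7- to 19-fold at the Table 3 locks (about 6-fold in Croatia if a year is lost to the history rule). The ratio would still be about 2.7 to 5.9 if data ran to March 2025, which is an assumption. At an unchanged prescribing rate the counts would fall by about 95%, 92% and 86% in the first case. The SMD compares shares and does not address a number, and for Objective 3 it is computed in a cohort that matches neither hypothesis. The 60% and 70% first-line shares and the 100 starters a month are illustrations only. The total number of new users is not left unexamined, since Objectives 1 and 6 cover it.

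**What to change.** 1. State one Objective 3 hypothesis in Tables 1 and 11: the proportion of new NOMAC or CMA users with a prior record of meningioma will be lower after the restrictions. Assess it separately in the NOMAC and CMA new-user cohorts already built for Objectives 2, 4 and 5, not in the combined any-class cohort. Bring the abstract's exposure entry for Objective 3 into line with the main text.
2. Reword Objective 4 in both tables as the proportion of new users who start as first-line. Read it mainly in the high-dose stratum, which Section 8.8 already plans and to which Section 6 says the first-line restriction applies.
3. For both, report the pre and post proportions and their difference with a 95% CI beside the SMD. Where a cell is below 5 and masked under Section 8.8, withhold the interval too, because with a known denominator it could reveal the count.
4. Leave falls in the number of new users to the incidence rates of Objectives 1 and 6.

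The cost is a wording change in two tables and the abstract, one extra characterisation of existing cohorts, and an interval per proportion. The downside is that intervals for meningioma will be wide or suppressed.
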